## Appendix 2                      RHPATH[1-84] AND SUPPLEMENT TITRATION GUIDELINE

In this study the goal is to continue rhPTH[1-84] dosing and to reduce calcitriol and oral calcium (carbonate or citrate) supplementation to as low as safely possible, while maintaining total serum calcium levels. In patients with hypoparathyroidism treated with oral calcium and calcitriol, it is suggested to maintain total serum calcium levels in the lower half of the normal range (eg, between 8.0 and 9.0 mg/dL; [Shoback 2008](#)). This is to reduce symptoms and to avoid the hypercalciuria which can occur in the hypoparathyroid patient on calcitriol and oral calcium supplementation ([Horwitz and Stewart 2008](#)). In the current trial, all subjects will receive rhPTH[1-84]. Hence, down-titration of calcitriol and oral calcium must be undertaken, where appropriate, to avoid hypercalcemia. At all times, changes in calcitriol and oral calcium dosing should be undertaken at the discretion of the investigator, based on total serum calcium concentrations and the subject's clinical condition.

To help facilitate a more standardized approach to dose adjustment across study centers, the following guideline has been prepared. The guideline is non-mandatory but the approach suggested should be assessed when adjustments in calcitriol and oral calcium are being considered. In the guideline, all references to total serum calcium levels indicate "predose" (trough) values drawn prior to administration of study drug, rhPTH[1-84] (ie, approximately 23 to 24 hours after the previous injection).

The order and magnitude of subsequent reductions in either calcitriol or oral calcium supplementation is left to the investigator's discretion, based on individual subject response. After any change in the rhPTH[1-84] dose, or a significant change in calcitriol or oral calcium supplement dose, a total serum calcium level **MUST** be measured 3 to 5 days later for safety purposes (unless earlier or more frequent testing is clinically required) and to guide further changes in supplement doses.

At the end of the study (this includes any subject that terminates early) subjects must be assessed clinically at their study center to ensure that they return safely to an appropriate calcium and calcitriol supplementation level. This includes the performance of necessary testing for total serum calcium 3 to 5 days later for safety purposes (unless earlier or more frequent testing is clinically required) to ensure a stable total serum calcium level has been achieved. The completion of these procedures should be documented by the site.

### Significant Hypercalcemia

Any instances of significant hypercalcemia, which is defined as any total serum calcium level of > 11.9 mg/dL (even on a non-trough measurement), require **MANDATORY** immediate stopping of rhPTH[1-84] treatment. Suspension of dosing with calcitriol and oral calcium as clinically appropriate and testing of serum total calcium levels at least daily should be undertaken until the subject's serum total calcium returns to the normal range. Other clinically appropriate actions for the treatment of significant hypercalcemia should be undertaken as usual by the investigator to ensure subject safety. Thereafter, rhPTH[1-84] can be reintroduced with clinically appropriate doses of calcitriol and oral calcium, with the aim to avoid further episodes of abnormal serum calcium.

## Hypocalcemia

If the total serum calcium level falls below 8.0 mg/dL (or below the baseline values, if the subject entered the study with a total serum calcium < 8.0 mg/dL), then the subject's calcitriol and oral calcium doses should be checked and the injection technique of rhPTH[1-84] reviewed with the subject to ensure proper administration. At planned study visits (Week 4, 8 etc) the rhPTH[1-84] dose can be uptitrated if indicated in the opinion of the investigator following discussion with the sponsor. During interim safety checks, hypocalcemia should be addressed by clinically indicated increases in calcitriol or supplemental oral calcium doses according to the guideline below, with the goal of attaining a total serum calcium level of 8.0 to 9.0 mg/dL. Laboratory testing should be repeated as indicated in order to ensure that changes in dosing are accompanied by improved serum calcium levels.

Visit number	Serum calcium (mg/dL)	rhPTH[1-84] dose	Supplement dose adjustment
Visit 1 (Baseline)	> 9.5 mg/dL and < 500 mg supplemental oral calcium and no calcitriol	Start at 25 µg	Receive no supplemental calcitriol and oral calcium
	> 9.5 mg/dL on any dose of supplemental calcitriol or ≥ 500 mg oral calcium	Start at 50 µg	Stop supplemental calcitriol and oral calcium
	≤ 9.5 mg/dL on any dose of supplemental calcitriol or oral calcium	Start at 50 µg	Maintain supplemental calcitriol and oral calcium
Interim Safety Check: * 3-5 days post Visit 1  AND  * after significant change in supplements  *or after any adjustment in rhPTH[1-84] dose *or if clinically indicated	< 8.0 mg/dL	Maintain	Increase calcitriol dose or oral calcium dose as required*
	8.0 - 9.0 mg/dL	Maintain	No change in calcitriol dose; no change in oral calcium dose
	9.1 - 10.5 mg/dL	Maintain	Reduce calcitriol dose by up to 50%; if no longer receiving calcitriol then reduce oral calcium dose by up to 50% *
	10.6 - 11.9 mg/dL	Maintain	Reduce by up to 50% or eliminate calcitriol dose and/or oral calcium dose *
	> 11.9 mg/dL	Stop Study Drug until serum calcium is in the normal range on at least daily retesting	STOP calcitriol AND oral calcium dosing until serum calcium is in the normal range on at least daily retesting

At baseline, the starting dose should be 25 or 50 µg/d, as no experience is available with a higher starting dose. A stepwise dose increase of rhPTH[1-84] is advised if needed after an observation of the initial response to 25 or 50 µg/d.

Visit number	Serum calcium (mg/dL)	rhPTH[1-84] dose	Supplement dose adjustment
Weeks 4 to End of Study	< 8.0 mg/dL	Uptitrate	Reduce calcitriol dose by up to 50% (if not receiving calcitriol, reduce oral calcium dose by up to 50% as required) *
	8.0 - 9.0 mg/dL	Maintain	No change in calcitriol dose; no change in oral calcium dose
	9.1 - 10.5 mg/dL	Maintain	Once both calcitriol and calcium doses have been reduced by $\geq 50\%$ from Baseline, further reduction or elimination of calcitriol and reduction of oral calcium to 500mg/day can be made at the investigator's discretion based on serum calcium levels*
	10.6 - 11.9 mg/dL	Maintain	
	> 11.9 mg/dL	Stop rhPTH[1-84] until serum calcium is in the normal range on at least daily retesting	STOP calcitriol AND oral calcium dosing until serum calcium is in the normal range on at least daily retesting

\* Any changes in the rhPTH[1-84] dose or calcitriol and/or oral calcium supplement dose must be followed by a safety laboratory check for total serum calcium 3 to 5 days afterwards (or earlier if deemed clinically necessary). The safety laboratory checks can be performed using a local laboratory.

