### 3 STUDY DESIGN

#### 3.1 Overall Design and Control Methods

This study is a long-term, open-label study using rhPTH[1-84] for the treatment of adult male and female subjects with hypoparathyroidism. The subjects must have previously completed the NPSP558 RELAY study (8 weeks of active therapy) and/or previously completed the NPSP558 REPLACE study (CL1-11-040) (Visit 18).

The goal of this study is to optimize rhPTH[1-84] dosing while reducing calcitriol and oral calcium (carbonate or citrate) supplementation to as low as safely possible while maintaining total serum calcium levels (see [Appendix 2](#), rhPTH[1-84] and Supplement Titration Guideline).

- The starting dose of rhPTH[1-84] for this study will be 25 or 50 µg SC once daily (QD).
- Subjects with a total serum calcium value of  $\leq 9.5$  mg/dL will have a starting dose of 50 µg.
- Subjects with a total serum calcium value of  $> 9.5$  mg/dL will have a starting dose as follows:
  - Subjects who are taking supplements ( $\geq 500$  mg calcium and/or any calcitriol) will have the supplements reduced or stopped and will start at a dose of 50 µg SC QD.
  - Subjects who are taking minimal or no supplemental calcium ( $< 500$  mg) and no calcitriol will have a starting dose of 25 µg SC QD.
- Study visits during the first 12 months of the study will be conducted at Weeks 1 (baseline), 4, 8, and then every 8 weeks thereafter up to Week 48 (Visit 8). The Week 52 visit (Visit 9) is scheduled 4 weeks later.
- At the end of Week 52, subjects will be invited to extend their study drug regimen until January 2018 or after the completion of the last patient's Month 72 visit, whichever comes last. During this time, subjects will return to the clinic for interim visits every 2 months (Months 14, 16, 18, etc).
- All subjects will have their total serum calcium checked by a local laboratory 3 to 5 days ( $\pm 2$  days) following the baseline visit.
- Subjects may have their rhPTH[1-84] dose increased in increments of 25 µg to a maximum of 100 µg SC QD by the investigator at any time during the study, with the goal of achieving or maintaining total serum calcium levels in the range of 8.0 to 9.0 mg/dL. The rhPTH[1-84] dose may be adjusted downward at any time as needed to maintain appropriate serum calcium levels (approximately 8.0 to 9.0 mg/dL) or due to any safety concerns.

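### At a scheduled visit with serum calcium below 8.0 mg/dL, the titration table cuts supplements whether or not rhPTH[1-84] is raised, so a subject already at 100 µg is left with only a cut

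*Protocol*

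**What the plan says.** Protocol Appendix 2 gives two sets of titration rules.

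- **Weeks 4 to End of Study table, calcium below 8.0 mg/dL.** The rhPTH[1-84] column says to uptitrate. The supplement column says "Reduce calcitriol dose by up to 50% (if not receiving calcitriol, reduce oral calcium dose by up to 50% as required".
- **Interim Safety Check rows, calcium below 8.0 mg/dL.** The rhPTH[1-84] column says to maintain the dose. The supplement column says "Increase calcitriol dose or oral calcium dose as required".

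Section 3.1 allows dose increases in 25 µg steps "to a maximum of 100" µg daily. The Hypocalcemia text in Appendix 2 makes uptitration at planned visits optional: the "dose can be uptitrated if indicated in the opinion of the investigator following discussion with the sponsor". It directs supplement increases only for interim safety checks. It also asks for a dosing response that raises calcium: "Laboratory testing should be repeated as indicated in order to ensure that changes in dosing are accompanied by improved serum calcium levels".

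The introduction to Appendix 2 explains why supplements come down: "down-titration of calcitriol and oral calcium must be undertaken, where appropriate, to avoid hypercalcemia". It also sets the status of the guideline: "The guideline is non-mandatory but the approach suggested should be assessed when adjustments in calcitriol and oral calcium are being considered". The table footnote says that any dose change "must be followed by a safety laboratory check for total serum calcium 3 to 5 days afterwards".

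**The concern.** Raising rhPTH[1-84] while lowering supplements fits the aim of the study, and that pairing is not in question. The difficulty is that the supplement cell stands alone. Nothing in it says that the cut applies only if the dose has gone up, and no row, footnote or text in Appendix 2 covers a subject who is below 8.0 mg/dL at a planned visit and cannot be, or is not, uptitrated.

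The clearest case is a subject already at 100 µg. This is foreseeable: Section 2.2 makes safe long-term use of 25 to 100 µg a secondary objective, and the row applies from Week 4 for up to 80 months of treatment (Section 3.2). The same gap exists, less strongly, when the optional uptitration is not made.

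At stake is hypocalcemia, a named safety endpoint (Section 2.3.1) in a study whose primary objective is safety. In this case the row points away from the 8.0 to 9.0 mg/dL target.

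**Working it through.** The plan states no figure to reproduce, so the main check is to apply the two rows for calcium below 8.0 mg/dL at each permitted dose.

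| Current rhPTH[1-84] dose | Weeks 4+ row: dose | Weeks 4+ row: supplements | Interim row: dose | Interim row: supplements |
|---|---|---|---|---|
| 25 µg | to 50 µg | cut by up to 50% | hold | increase |
| 50 µg | to 75 µg | cut by up to 50% | hold | increase |
| 75 µg | to 100 µg | cut by up to 50% | hold | increase |
| 100 µg | no increase possible | cut by up to 50% | hold | increase |

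In the first three lines the two rules differ because the dose action differs. In the last line the dose is 100 µg before and after under both rules, and the calcium band is the same, yet the supplement instructions are opposite. Followed literally, the tables would cut supplements at the visit and then, if calcium were still below 8.0 mg/dL at the recheck, raise them again.

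The stated reasons for cutting do not reach this case. Avoiding hypercalcemia does not apply below 8.0 mg/dL with no dose increase. The wider aim in Appendix 2 of minimizing supplements is limited to what is safe and keeps serum calcium maintained.

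**Size of the permitted cut**

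- Calcitriol: 0 to 50% of the current dose.
- Oral calcium, if not on calcitriol, at the 500 mg/day goal (Section 3.1): 500 × 0.5 = 250 mg/day.
- Oral calcium, outer range, borrowing the conventional-therapy doses in Section 1.2: 2000 × 0.5 = 1000 mg/day to 3500 × 0.5 = 1750 mg/day. The documents do not give supplement doses for subjects at 100 µg, so this range is an assumption and probably an overstatement.

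**Duration**

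- The recheck falls at 3 to 5 days, that is 72 to 120 hours.
- Section 1.1 gives 1,25(OH)₂ vitamin D a half-life of about 6 hours: 72 / 6 = 12 and 120 / 6 = 20 half-lives.
- The lower supplement-derived level is therefore reached before the recheck. This does not show how far serum calcium would fall, and no document gives that.

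**Frequency.** The documents give no basis for estimating how many subjects would be below 8.0 mg/dL at a scheduled visit without a dose increase.

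**The case against.** The strongest reply is that the row is one joint step. If its first half cannot be carried out, a sensible investigator concludes that the row does not fit, rather than carrying out its second half alone.

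Other text points the same way:

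- The guideline is non-mandatory, and supplement changes are at the investigator's discretion in light of serum calcium and clinical condition.
- A cut of zero satisfies the wording.
- The interim rows may also be used when clinically indicated.
- Supplement doses and injection technique are to be checked at any low value.
- A recheck is required within days of any change.

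On this view the point is an unaddressed edge case that touches no endpoint definition, estimate or mandatory rule.

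Much of this stands. It limits the likely harm, and most investigators would probably not make the cut. The objection is also right that the half-life arithmetic and the outer calcium range add little.

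What it does not do is supply the missing condition. Appendix 2 says it was written to standardize dose adjustment across centers, and a row that works only if investigators disregard half of it does not serve that purpose. The recheck shortens the exposure but does not prevent it.

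**Conclusion.** The concern holds and should be fixed. For a subject below 8.0 mg/dL at a scheduled visit whose rhPTH[1-84] dose is not raised, and most clearly one already at 100 µg, the only supplement instruction in the row is a cut. The protocol's own interim rule for the same calcium band with the dose held is an increase.

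The size is modest: up to half the calcitriol dose, or up to 250 mg/day of oral calcium at the study goal, for 3 to 5 days if the recheck is on time and the interim row is then followed. The conclusion rests on a literal reading of the row and on the absence of any text covering this case. It does not rest on an assumed frequency or on an assumed fall in serum calcium. Confidence is high that the condition is missing; the expected clinical harm is small.

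**What to change.** Split the below 8.0 mg/dL row of the Weeks 4 to End of Study table in two:

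1. **rhPTH[1-84] increased at this visit:** supplements may be reduced as now written.
2. **Subject at 100 µg, or dose not increased:** do not reduce supplements. Raise calcitriol or oral calcium as needed, as in the interim row for the same calcium band, and recheck total serum calcium in 3 to 5 days.

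The cost is one added line in one Appendix 2 table, made by amendment or by a clarification letter to sites. It needs no new visits, procedures or samples.

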### **Appendix 3                    METHOD OF BIRTH CONTROL**

Women of childbearing potential must consent to use 2 acceptable methods of birth control from the list below:

- Hormonal methods of contraception such as oral, injected, vaginal rings, transdermal patch, implanted.
- Placement of an intrauterine device (IUD) or intrauterine system (IUS).
- Barrier methods of contraception: Condom or occlusive cap (diaphragm or cervical/vault caps) with spermicidal foam/gel/film/cream/suppository.
- Male partner sterilization (vasectomy).

Male subjects with female partners of childbearing potential together also must use 2 acceptable forms of contraception during the subject's participation.

## Appendix 4                      PROTOCOL HISTORY

NPS Pharmaceuticals, the original sponsor of this study, was acquired by Shire Pharmaceuticals on 21 February 2015.

Document	Date	Global/Country/Site Specific
Original Protocol Version 1.0	30 December 2010	Global
Amendment 1 Version 2.0	29 June 2011	
Amendment 2 Version 3.0	05 October 2011	
Amendment 3 Version 4.0:	15 March 2012	
Site Amendment 4 Version 5.0	30 May 2013	Site-Specific
Amendment 5	3 May 2016	Global
Amendment 6	24 October 2016	Global

Amendment 1 v2.0	22MAR2018	PPD	Study design description and schedule tables were updated to be aligned with Protocol Amendment 6.

List of abbreviations and definition of terms

AE	Adverse Event
AESI	Adverse Event of Special Interest
ALT	Alanine Aminotransferase
AST	Aspartate Aminotransferase
ATC	Anatomic Therapeutic Chemical classification
BMD	Bone mineral density
BMI	Body Mass Index
BSAP	Bone-specific alkaline phosphatase
BUN	Blood Urea Nitrogen
CBC	Complete blood count
CPK	Creatine phosphokinase
CTx	C-terminal telopeptide of type 1 collagen
DSMB	Data and Safety Monitoring Board
DXA	Dual-energy x-ray absorptiometry
ECG	Electrocardiogram
ECP	Escherichia coli protein
EOT	End of Treatment
eCRF	Electronic case report form
CLcr	Cockcroft-Gault Creatinine Clearance
FDA	Food and Drug Administration
FSH	Follicle-stimulating hormone
GFR	Glomerular filtration rate
GI	Gastrointestinal
HR	Heart Rate
ICF	Informed consent form
ICH	International Conference on Harmonization
ITT	Intent-to-Treat
IVR	Interactive Voice Response
IWR	Interactive Web Response
LDH	Lactate dehydrogenase
MedDRA	Medical Dictionary for Regulatory Activities
ms	milliseconds
NDA	New Drug Application
P1NP	Procollagen amino-terminal peptide
PR	In electrocardiography, the time from the beginning of the P wave (onset of atrial depolarization) to the beginning of the QRS complex
PT	Preferred Term
PTH	Parathyroid hormone
QD	Daily
QRS	In electrocardiography, the QRS complex represents the time it takes for depolarization of the ventricles
QT	In electrocardiography, the time from the beginning of the QRS complex to the end of the T wave
QTc	QT interval corrected for heart rate
QTcB	QT corrected for heart rate by the Bazett method
QTcF	QT corrected for heart rate by the Fridericia method
RBC	Red Blood Cell
RELAY	A Randomized, Dose-blinded Study to Investigate the Safety and Efficacy of NPS558, a Recombinant Human Parathyroid Hormone (rhPTH[1-84]), at Fixed Doses of 25 µg and 50 µg for the Treatment of Adults With Hypoparathyroidism. Study No. is PAR-C10-007
REPLACE	A Randomized, Double-blind, Placebo-Controlled, Phase 3 Study to Investigate the Use of NPS558, a Recombinant Human Parathyroid Hormone (rhPTH[1-84]) for the Treatment of Adults with Hypoparathyroidism. Study No. is CL1-11-040
rhPTH	Recombinant human parathyroid hormone
RR	In electrocardiography, the time duration between two consecutive R waves

SAE	Serious Adverse Event
SAP	Statistical Analysis Plan
SC	Subcutaneous
SI	International System of Units
SOC	System Organ Class
TEAE	Treatment Emergent Adverse Event
TESAE	Treatment Emergent Serious Adverse Event
ULN	Upper Limit of Normal
WBC	White Blood Cell
WHO	World Health Organization

1. Introduction

This document describes the rules and conventions for data handling and methodologies for statistical analysis to be used in the presentation and analysis of efficacy and safety data for protocol PAR-C10-008 (RACE). It describes, in detail, the data and variables to be summarized and analyzed, including specifics of the statistical analyses to be performed. This statistical analysis plan is based on Protocol Amendment 6, dated October 24, 2016.

Hypoparathyroidism is a condition in which there is deficient production of parathyroid hormone (PTH) from the parathyroid glands. The deficiency of PTH results in decreased calcium reabsorption from renal tubules, malabsorption of calcium from the gastrointestinal (GI) tract and reduced calcium mobilization from bone. Hypoparathyroidism is the most common cause of chronic hypocalcemia.

NPSP558 (rhPTH[1-84]) is recombinant human parathyroid hormone that is identical in structure to endogenous human parathyroid hormone (hPTH), a single-chain polypeptide consisting of 84 amino acid residues (rhPTH[1-84]). This is a 12-month open-label study investigating the safety and tolerability of NPSP558 for the Treatment of Adults with Hypoparathyroidism.

A Phase 3 study is currently ongoing (CL1-11-040, REPLACE) to investigate the effects of daily subcutaneous (SC) injections of rhPTH[1-84] at doses of 50, 75, or 100 µg. An 8-week study of fixed doses of 25 and 50 µg (PAR-C10-007, RELAY) is currently being undertaken to explore a broader range of treatment dose options.

2. Study Objectives

2.1. Primary objective

To demonstrate the long-term safety and tolerability of SC rhPTH[1-84] as hormone replacement therapy for the treatment of adult subjects with hypoparathyroidism.

2.2. Secondary objective

- To evaluate the impact of different preparations of calcium on the response to rhPTH[1-84] replacement therapy
- To demonstrate that dosing with rhPTH[1-84] across a dose range of 25 to 100 µg SC can be implemented in a safe and effective manner and can be maintained throughout long-term treatment
- To evaluate the impact of calcium-sparing diuretics on serum and urinary calcium

3. Study Design

3.1. General Description

This study is a long-term, open-label study using rhPTH[1-84] for the treatment of adults with hypoparathyroidism. Subjects can enroll if they either previously completed the NPSP558 RELAY study (PAR-C10-007) (8 weeks of active therapy) and/or completed the REPLACE study (CL1-11-040) (Visit 18).

The goal of this study is to optimize rhPTH[1-84] dosing while reducing calcitriol and oral calcium (carbonate or citrate) supplementation to as low as safely possible and maintaining total serum calcium levels. Dose adjustments to rhPTH[1-84] and to the calcium/calcitriol supplements and safety monitoring of calcium levels are explained in protocol Appendix 2, rhPTH[1-84] and Supplement Titration Guideline.

- The starting dose of rhPTH[1-84] for this study will be 25 or 50 µg SC once daily (QD)
- Subjects may have their rhPTH[1-84] dose adjusted by the investigator at any time during the study, with the goal of achieving or maintaining total serum calcium levels in the range of 8.0 to 9.0 mg/dL.
- If **ANY** predose (trough) total serum calcium is >11.9 mg/dL study drug will be stopped.
- Subjects will have blood draws to assess total serum calcium levels (which may be performed locally) 3 to 5 days after **ANY** dose adjustment of rhPTH[1-84], after any significant change in doses of calcium and/or calcitriol supplements, or at any other time at the discretion of the investigator.
- Study visits during the first 12 months of the study will be conducted at Weeks 1 (baseline), 4, 8, and then every 8 weeks thereafter up to Week 48 (Visit 8). The Week 52 visit (Visit 9) is scheduled 4 weeks later.
- At any time following the Week 16 (Visit 4), subjects who are on a stable dose of rhPTH[1-84] and have a 24-hour urine calcium >300 mg (males) and >250 mg (females) may be treated for hypercalciuria with calcium-sparing diuretics, if this therapy had not been introduced prior to the study.
- At the end of Week 52, subjects will be invited to extend their study drug regimen until January 2018 or after the completion of the last patient's Month 72 visit, whichever comes last..
- During this time, subjects will return to the clinic for interim visits every 2 months (Months 14, 16, 18, etc).
- After the End of Treatment visit or early termination visit, subjects who will not continue rhPTH[1-84] treatment will have their total serum calcium and phosphate levels measured 3 to 5 days after the last dose of study medication. Doses of calcium and active vitamin D supplements will be adjusted by the Investigator as appropriate. Thereafter, the Investigator will repeat serum calcium/phosphate monitoring and supplement dose adjustments as appropriate to achieve target serum calcium/phosphate concentrations until the follow up phone call 4 weeks ± 7days after end of treatment visit. After the 4 weeks follow up phone call, further management of hypoparathyroidism will occur as part of the subject's long-term non-study medical care.

A schematic presentation of the study design is displayed in Figure 1.1 and Figure 1.2.

Figure 1.1 Study Design – First 12 Months of Study

[figure not shown]
[figure not shown]

Figure 1.2 Study Design – Long-term Extension

